#### **5.4.2     *Concomitant Therapy to be used with Caution***

Medications that are CYP2C9, CYP3A4, or BCRP substrates with a narrow therapeutic index should be used with caution (Refer to [Appendix 2](#) for a list of these medications).

In addition, medications that are known to increase the risk of seizures should be used with caution.

#### **5.4.3     *Permitted Concomitant Therapy***

Medications and treatments other than those specified in [Section 5.4.1](#) and [Section 5.4.2](#), including palliative and supportive care for disease-related symptoms are permitted.

Patients should be closely monitored, and treatment is to be instituted for disease-related symptoms as appropriate. Supportive care measures for treating AEs should be instituted as soon as they are recognized.

Anti-emetic treatments may be used at the Investigator's discretion and in accordance with the American Society of Clinical Oncology guidelines or equivalent after documented nausea or vomiting has occurred without medications having been used. The choice of anti-emetic treatment, if required, will be made at the Investigator's discretion. Prophylaxis for nausea, vomiting, and diarrhea may be given as needed.

### **5.5     Additional Precautions**

The light absorption characteristics of avapritinib suggest the possibility the avapritinib treatment will be associated with phototoxicity. Therefore, patients should use clothing and sunscreen to avoid direct sun exposure.

Avapritinib treatment has been associated with seizures at high doses in toxicology studies in rats, and with intracranial bleeding in toxicology studies in dogs. There have been cases of intracranial bleeding in patients treated with avapritinib. Therefore, patients at increased risk of seizure, or increased risk of intracranial bleeding (such as those with a vascular aneurysm or a history of intracranial bleeding within the prior year) should only receive avapritinib if the potential benefits are anticipated to exceed the increased risk.

#### **5.5.1     *Contraception Requirements***

Women of childbearing potential must agree to use a highly effective method of contraception ([CTFG, 2014](#)) from the time of enrollment until at least 30 days after the last dose of avapritinib. Women are considered to be of childbearing potential after

menarche until becoming postmenopausal (defined as no menses for at least 12 months without an alternative medical cause) unless permanently sterile. A high follicle stimulating hormone level in the postmenopausal range may be used to confirm a postmenopausal state in women not using hormonal contraception or hormonal replacement therapy. However, in the absence of 12 months of amenorrhea, a single follicle stimulating hormone measurement is insufficient. Permanent sterilization methods include hysterectomy, bilateral salpingectomy and bilateral oophorectomy ([CTFG, 2014](#)). Because avapritinib and regorafenib are potential CYP3A4 inducers, women should use hormonal contraception with caution and supplement with other highly effective methods.

Males with partners who are female of reproductive potential must agree that they will use condoms, and their partners will use a highly effective contraceptive method throughout their participation in the Study, and for 90 days after the last dose of avapritinib. Highly effective forms of contraception are defined as the following ([CTFG, 2014](#)):

- Combined (estrogen and progestogen containing) hormonal contraceptives that inhibit ovulation, including oral, intravaginal and transdermal products;
- Progestogen-only hormonal contraceptives that inhibit ovulation, including oral, injectable, and implantable products;
- Intrauterine devices (IUD) and intrauterine hormone-releasing system (IUS);
- Bilateral tubal occlusion (women);
- Male partner vasectomy or other method of surgical sterilization provided that the partner is the sole sexual partner of the trial participant and the vasectomized partner has received medical assessment of the surgical success;
- Sexual abstinence (men and women), when this is the preferred and usual lifestyle of the patient. Periodic abstinence (such as calendar, symptothermal and postovulation methods), withdrawal (coitus interruptus), and the lactational amenorrhea method are not acceptable methods of contraception.

The following methods of contraception are not considered highly effective ([CTFG, 2014](#)):

- Progesterone-only oral hormonal contraception that do not inhibit ovulation;
- Barrier methods with or without spermicide, or spermicide alone.

### **5.5.2 Gamete and Embryo Banking**

Hypospermatogenesis was observed in the testis and epididymis of rats and dogs and did not recover after 2-week recovery. Patients should be reminded of the possibility of gamete and embryo banking.

## **6 DESCRIPTION OF STUDY PROCEDURES**

Upon entry into the Study, the following baseline procedures and laboratory tests are to be performed before treatment with avapritinib is initiated. Please refer to [Table 1](#) for the Schedule of Assessments.

### **6.1 Assessment Prior to Initiating Treatment**

The following procedures will be performed at the Screening visit:

- Obtain Informed Consent;
- Obtain demographic data, including gender, date of birth/age, race, and ethnicity;
- Complete physical examination, basic neurological assessment, and ECOG performance status;
- Vital signs including height, weight, temperature, pulse, and systolic/diastolic blood pressure;
- Clinical laboratory assessment (hematology, coagulation, serum chemistry);
- Serum pregnancy test (for women of childbearing potential only);

### **6.2 Safety Assessments**

The schedule of safety assessments is detailed in [Table 1](#). Additional safety assessments may be performed when clinically indicated, at the Investigator's discretion.

#### **6.2.1 Physical Examination**

A complete physical examination will be performed at the Screening visit. Subsequent physical examinations will be performed as outlined in [Table 1](#), and will focus on symptoms and signs of GIST, changes from previous physical examinations, and AEs.

#### **6.2.2 Eastern Cooperative Oncology Group Performance Status**

Determination of ECOG performance status will be performed at the time points outlined in [Table 1](#). Refer to [Appendix 3](#) for ECOG performance status scoring.

### **6.2.3 Vital Signs**

Vital sign measurement will include temperature, systolic/diastolic blood pressure, and pulse, and will be performed at the time points outlined in [Table 1](#).

### **6.2.4 Clinical Laboratory Tests**

Clinical laboratory evaluations will be performed at the local laboratory.

Clinical laboratory evaluations will be conducted at the time points outlined in [Table 1](#). In addition, all clinically significant laboratory abnormalities noted on testing will be followed by repeat testing and further investigated according to the judgment of the Investigator.

The following safety laboratory parameters are to be evaluated by the Investigator:

**Hematology:** Hemoglobin (Hgb), white blood cell with differential count, platelet count

**Serum chemistry:** Sodium, potassium, blood urea nitrogen or urea, bicarbonate (venous), creatinine, calcium, chloride, magnesium, phosphorus, albumin, AST, ALT, alkaline phosphatase, and total bilirubin (direct bilirubin if total bilirubin is > ULN)

**Serum or Urine**  $\beta$ -hCG

**Pregnancya:**

a For women of childbearing potential only, as defined in [Section 9.6](#). A serum pregnancy test should be performed at baseline (within 7 days before the first dose of avapritinib). Serum or urine pregnancy test should be performed as required per local regulations and as outlined in [Table 1](#).

### **6.2.5 Adverse Events and Concomitant Medications**

Each patient must be carefully monitored for the development of any AEs throughout the study from the start of avapritinib administration (or from the time of signing informed consent, for SAEs) to 30 days after the last administration. In addition, SAEs that are assessed to be at least possibly related to Study treatment that occur > 30 days posttreatment are to be reported.

Adverse events will be recorded locally, but only SAEs will be reported to the sponsor or its designee. Complete details on AE and SAE monitoring are provided in [Section 8](#) and [Section 9](#), respectively.

Concomitant medications will be recorded from the time of signing informed consent to 30 days after the last dose.

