## 8 ADVERSE EVENTS

All patients will be monitored for adverse events throughout their participation in the Study. Serious AEs and adverse events of special interest (AESIs) will be recorded in the CRF from the time of first dose of avapritinib through 30 days after the last avapritinib dose. In addition, serious adverse events (SAEs) and AESIs that are assessed as related to avapritinib treatment and that occur > 30 days posttreatment will also be reported. All related SAEs and AESIs should be monitored until they are resolved, stabilized, have returned to pre-exposure baseline, determined to be due to another illness, or until a subsequent therapy is initiated.

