### **9.3 Documenting Serious Adverse Events and Adverse Events of Special Interest**

Each patient must be carefully monitored for the development of any SAEs and AESIs, Adverse Events of Special Interest for avapritinib are, regardless of grade or causality:

- cognitive effects which include the following terms: memory impairment, cognitive disorder, confusional state and encephalopathy.
- intracranial bleeding including haemorrhage intracranial, cerebral haemorrhage, and subdural haematoma.

This information should be obtained in the form of non-leading questions (eg, “How are you feeling?”) and from signs and symptoms detected during each examination, observations of study personnel, and spontaneous reports from patients.

All SAEs and AESIs reported by the patient or revealed by observation, physical examination, laboratory testing or other diagnostic procedures will be recorded in the appropriate section of the CRF. When possible, signs and symptoms indicating a common underlying pathology should be noted as one comprehensive event.

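### The protocol gives conflicting rules on whether SAEs are in the CRF, when SAEs and AESIs are collected, and whether non-serious AESIs reach the sponsor

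*Combined protocol and SAP*

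**What the plan says.** Section 2 makes the rate of SAEs and AESIs an objective. The Protocol Summary plans the proportion of patients with each, among those who receive at least one dose, and Section 10 plans summaries by system organ class and preferred term.

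**Where SAEs are held.** Section 8: "Serious AEs and adverse events of special interest (AESIs) will be recorded in the CRF". Section 9.3 says that all SAEs and AESIs found by patient report, examination, laboratory or other "diagnostic procedures will be recorded in the appropriate section of the CRF". Section 9.2 says the opposite for SAEs: they are held in the safety database alone and kept out of the CRF.

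**When events are collected.** Table 1 footnote k collects SAEs and AESIs from the date of consent through end of treatment. Section 8 records both "from the time of first dose of avapritinib through 30 days after the last avapritinib dose". Section 6.2.5 monitors adverse events from the start of avapritinib, "or from the time of signing informed consent, for SAEs) to 30 days after the last administration". Section 9.2 also makes serious pretreatment events reportable.

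**What reaches the sponsor.** Section 6.2.5: "Adverse events will be recorded locally, but only SAEs will be reported to the sponsor or its designee". For late events it says only that "SAEs that are assessed to be at least possibly related to Study treatment that occur > 30 days posttreatment are to be reported". Section 9.3 sets a wide scope for AESIs: "Adverse Events of Special Interest for avapritinib are, regardless of grade or causality". Section 8 extends late reporting to them: "AESIs that are assessed as related to avapritinib treatment and that occur > 30 days posttreatment will also be reported".

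**The concern.** SAEs and AESIs are the study's main output; the Protocol Summary says that response will not be collected. A site cannot both enter SAEs in the CRF and leave them out. It also cannot tell which start and end dates apply, or whether a low-grade memory complaint stays in the local record or goes to the sponsor.

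The stake is the completeness of the SAE and AESI tables. Three kinds of event are exposed: serious AESIs, if the AESI table is built from the CRF while SAEs are held elsewhere; events in screening or in the 30 days after the last dose; and non-serious AESIs. With about 5 patients, one missed patient visibly changes a proportion.

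**Working it through.** The plan has no figure to reproduce. Its number of patients is an estimate of how many will roll over, with no hypothesis test (Section 10). The check is a comparison of the sections, followed by one line of arithmetic.

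*Inputs.* About 5 patients (Section 4.1). Screening of up to 28 days (Table 1). A follow-up tail of 30 days after the last dose (Sections 6.2.5 and 8). AESIs of any grade or causality (Section 9.3).

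*Step 1, location of SAEs.* Sections 8 and 9.3 place SAEs in the CRF and Section 9.2 excludes them from it. The general rule in Section 11.4, that all patient data go onto CRFs, sides with the former. No reading lets a site satisfy both.

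*Step 2, windows.*

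| Event | Footnote k | Section 6.2.5 | Section 8 (CRF) |
|---|---|---|---|
| SAE during screening | in | in | out |
| Non-serious AESI during screening | in | out (AEs start at first dose) | out |
| SAE or AESI after end of treatment, within 30 days of last dose | out | in | in |
| Related SAE more than 30 days after treatment | out | reported | reported |
| Related non-serious AESI more than 30 days after treatment | out | not mentioned | reported |

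Followed literally, footnote k omits up to 30 days after the last dose, and Section 8 omits up to 28 days of screening. Both are upper limits: screening may be shorter, and Table 1 gives no day for the end-of-treatment visit.

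*Step 3, route for AESIs.* Because AESIs count at any grade, some will not be serious. Table 2 has rules for Grade 1 and Grade 2 cognitive or mood effects, so the protocol expects such events. Under Sections 8 and 9.3 they are CRF data. Under a literal reading of Section 6.2.5 they are adverse events that are not SAEs, and so remain local.

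*Step 4, size.* Suppose k of n patients have an AESI, and one whose only AESI is non-serious is not sent. The proportion changes by (k − 1)/n − k/n = −1/n.

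- n = 5: 1/5 = 20 percentage points; one affected patient in five (20%) becomes none (0%).
- n = 4: 1/4 = 25 points.
- n = 6: 1/6 = 16.7 points.

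The values 4 and 6 are assumptions that bracket the planned figure of about 5.

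**The case against.** The strongest reply concerns Section 6.2.5. Its next sentence sends the reader to Sections 8 and 9 for full details, and both collect AESIs. The headings of Sections 9.2 and 9.3 separate reporting SAEs from documenting SAEs and AESIs. On that reading, the sentence describes the 24-hour SAE route, and AESIs reach the sponsor through the CRF. This is plausible, and for that reason the sentence ranks third here. It does not remove the ambiguity: Section 8 uses the same verb for late AESIs, and Section 6.2.5 never mentions AESIs. A reader might infer that the protocol bars AESI data from the sponsor. The documents do not support that.

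Part of the mismatch before first dose may be one of purpose. Reporting serious events from consent while recording them in the CRF from first dose is not contradictory in itself. That answers Sections 6.2.5 and 9.2 against Section 8. It does not answer footnote k against Section 8, since both state when the same events are gathered.

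A reader might also add the two window gaps and express the sum as a share of follow-up. That would overstate the problem. The gaps lie at opposite ends, no single window omits both, and patient-days do not enter the planned proportions.

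Lastly, Section 10 names no data source, so the documents do not show that a serious AESI would be dropped from its table; that would require a table built from the CRF alone. The 1/n shift applies to any missed patient and says nothing about how likely a miss is. Both points stand.

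**Conclusion.** The concern holds as an internal inconsistency that should be fixed. In order of firmness:

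1. Section 9.2 and Sections 8 and 9.3 cannot both be followed on whether SAEs are in the CRF.
2. Footnote k and Section 8 give different start and end points for the same events. Each omits time that the other covers: up to 30 days after the last dose and up to 28 days of screening, respectively.
3. Section 6.2.5 is ambiguous on AESIs. If a site follows it literally, each patient whose only AESI is non-serious lowers the AESI proportion by 1/n, which is 20 percentage points at n = 5.

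The loss is conditional and no probability is claimed. The study manual (Section 9.2) and CRF guidelines (Section 11.4) are not in the documents and may contain a reconciliation, so it cannot be inferred that none is planned. The analysis is descriptive. Section 10 also treats these data as a continuation of the same patients' earlier studies, so one missed patient weighs less in that wider safety assessment than in this study's own table.

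**What to change.** - **SAE location.** Reconcile Section 9.2 with Sections 8 and 9.3. Either Section 9.2 allows SAEs in both the safety database and the CRF, or Sections 8 and 9.3 are corrected to leave them out. If they stay out, Section 10 should say that the SAE and AESI tables draw on the safety database and the CRF together, counting each patient once.
- **Windows.** Align Table 1 footnote k, Section 6.2.5 and Section 8 to one start and one end of collection for each event type.
- **AESI route.** Amend Section 6.2.5, for example: adverse events are recorded locally; SAEs go to the sponsor as described in Section 9.2; AESIs of any grade and causality go to the sponsor through the CRF as described in Section 9.3. Match its sentence on events more than 30 days after treatment to Section 8, so that related AESIs are included.

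The cost is wording changes in these sections and a routine reconciliation of the two sources for about 5 patients. No extra visits or patients are needed.

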## **6.3 Assessment of Response**

Investigator will perform assessment of response to treatment with avapritinib per local standard of care.

## 6.4 Patient Reported Outcome Instruments

No patient reported outcome instruments will be used in this study.

## 6.5 Data Collection and Reporting

Limited data will be collected from this study as the primary analysis has been completed for the initial clinical trials conducted in this setting. Nevertheless, adverse events will be reported and SAEs should be reported to the Sponsor, as required. Treatment records including record of drug dispensation shall be maintained to ensure appropriate drug accountability.

# 7 STUDY DRUG MANAGEMENT

## 7.1 Description

### 7.1.1 *Avapritinib*

#### 7.1.1.1 *Formulation*

Avapritinib will be administered as an immediate release tablet for oral administration. The drug substance and drug product are manufactured and formulated following current Good Manufacturing Practices (GMP). Avapritinib tablets are prepared as 100 mg in strength.

#### 7.1.1.2 *Storage*

Avapritinib tablets must be stored at 15°C to 30°C (59°F to 86°F), in their original container, according to the package label. If the product has been exposed to temperatures outside of this range, advice must be sought from the Sponsor as to whether the product is still suitable for patient use.

#### 7.1.1.3 *Packaging and Shipment*

Avapritinib tablets will be supplied in 60 cc Wide Mouth Round high-density polyethylene bottles. Each bottle will be induction-sealed and capped with a 33 mm child-resistant closure. Bottles will contain 30 tablets each.

## 7.2 Accountability

Accountability for avapritinib at the clinical site is the responsibility of the Investigator. The Investigator will ensure that avapritinib is used only in accordance with this protocol. Where allowed, the Investigator may choose to assign drug accountability responsibilities to a pharmacist or other appropriate individual.

The Investigator or delegate will maintain accurate drug accountability records indicating the drug's delivery date to the site, inventory at the site, use by each patient, and return to the Sponsor or its designee (or disposal of the drug, if approved by the Sponsor). These

records will adequately document that the patients were provided the doses as specified in the protocol and should reconcile all avapritinib received from the Sponsor.

Accountability records will include dates, quantities, batch/serial numbers, expiration dates (if applicable), and patient numbers. The Sponsor or its designee will review drug accountability at the site on an ongoing basis during monitoring visits.

Avapritinib must not be used for any purpose other than this Study. Avapritinib that has been dispensed to a patient and returned unused must not be re-dispensed to a different patient.

Patients will receive instructions for home administration of avapritinib.

All used, unused, or expired avapritinib will be returned to the Sponsor or its designee, or if authorized, disposed of at the clinical site per the site's Standard Operating Procedures and documented. All material containing avapritinib will be treated and disposed of as hazardous waste in accordance with governing regulations.

### **7.3 Compliance**

Patients will be dispensed the appropriate number of avapritinib bottles to allow for dosing until the next scheduled visit. Patients are to return all unused capsules and tablets (or the empty bottles) at the next scheduled visit. Compliance with the dosing regimen will be assessed based on return of unused drug (or empty bottles).

## 8 ADVERSE EVENTS

All patients will be monitored for adverse events throughout their participation in the Study. Serious AEs and adverse events of special interest (AESIs) will be recorded in the CRF from the time of first dose of avapritinib through 30 days after the last avapritinib dose. In addition, serious adverse events (SAEs) and AESIs that are assessed as related to avapritinib treatment and that occur > 30 days posttreatment will also be reported. All related SAEs and AESIs should be monitored until they are resolved, stabilized, have returned to pre-exposure baseline, determined to be due to another illness, or until a subsequent therapy is initiated.

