## 4.6 Patient Withdrawal Criteria

Patients have the right to withdraw from the Study at any time for any reason.

Patients must withdraw or be withdrawn from Study treatment for any of the following reasons:

- Withdrawal of consent;
- Pregnancy;
- Death.

Patients may withdraw or be withdrawn from Study treatment for any of the following reasons:

- AE;
- Disease progression;
- Protocol deviation;
- Investigator decision;
- Loss to follow-up.

When a patient discontinues Study drug, the primary reason(s) for discontinuation is to be recorded in the case report form (CRF). Following discontinuation of Study drug, all efforts will be made to complete and report the protocol-defined Study observations as completely as possible.

If a patient discontinues treatment because of an adverse event (AE), protocol-specified safety follow-up is to be performed, and the patient should remain under the supervision of the Investigator or designee until the condition has returned to baseline or stabilized.

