**Table 1: Schedule of Assessments**

Study Activities a	Screening	Treatment		EOT b
Cycle		C1	Every 3 months (+/- 15 days)	
Program Day	D0–28	D1	D1	
Informed consent	X			
Inclusion/Exclusion criteria	X			
Demographics	X			
Physical examination c	X	X	X	X
Vital signs d	X	X	X	X
ECOG status e	X			
Pregnancy ( $\beta$ -hCG) test f	X		X	
Hematology g	X	X	X	X
Serum chemistry h	X	X	X	X
Efficacy assessment i			Per Investigator discretion	
Avapritinib administration j		X		
SAE and AESI monitoring k		X		

Abbreviations: AE = adverse event; AESI = adverse event of special interest; ALP = alkaline phosphatase; ALT = alanine aminotransferase; aPTT = activated partial thromboplastin time; AST = aspartate aminotransferase;  $\beta$ -hCG = beta human chorionic gonadotropin; BUN = blood urea nitrogen; C = cycle, D = day, ECOG = Eastern Cooperative Oncology Group, EOT = end-of-treatment; GIST = gastrointestinal stromal tumor; Hgb = hemoglobin; INR = international normalized ratio; QD = once daily; SAE = serious adverse event; ULN = upper limit of normal.

a Additional safety tests may be performed whenever clinically indicated, at the Investigator's discretion. Whenever a test result is questionable, it should be repeated. Timing of procedures may be modified at Investigator discretion.

b At EOT, the reason for EAP discontinuation and last day of dosing should be recorded. This can be done by telephone if necessary.

c A complete physical examination including weight, evaluation of the skin, head and neck, lymph nodes, heart, lungs, breasts, abdomen, pelvis (if indicated based on symptoms), musculoskeletal system, neurologic system, and a basic assessment of mental status and mood will be performed at the Screening visit.

Subsequent physical examinations will focus on weight, signs of GIST, changes from previous physical examinations, neurologic, mental status, and mood examinations, and AEs.

d Vital signs include temperature, pulse, systolic/diastolic blood pressure, and weight.

e Refer to [Appendix 3](#) for ECOG performance status scoring.

f To be performed for women of child-bearing potential. A serum pregnancy test should be performed at baseline (within 7 days before the first dose of avapritinib). Serum or urine pregnancy test should be performed on D1 of every study visit, or more frequently if required by local requirements.

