## **9.5 Assessment of Causality**

Relationship to avapritinib administration will be determined by the Investigator according to the following criteria:

- Not Related: Exposure to avapritinib did not occur, or the occurrence of the AE is not reasonably related in time, or the AE is clearly caused by something other than avapritinib.
- Related: The AE does not meet the criteria for “Not Related”.

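### Sections 4.6 and 8 set different end points for following events ongoing at the last dose, and Table 1 schedules no post-treatment contact, so some SAE and AESI outcomes may go unrecorded

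*Combined protocol and SAP*

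**What the plan says.** Four parts of the protocol bear on what happens to an event still ongoing at the last dose.

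- **Section 8 (Adverse Events).** The follow-up rule reads "All related SAEs and AESIs should be monitored until they are resolved, stabilized, have returned to pre-exposure baseline", and continues with two further exits: "determined to be due to another illness, or until a subsequent therapy is initiated". Separately, SAEs and AESIs are recorded from first dose to 30 days after the last dose, with no causality condition. Those occurring later are reported if related.
- **Section 4.6 (Patient Withdrawal Criteria).** Anyone stopping for an adverse event is owed safety follow-up as laid down in the protocol. How long this lasts is put as follows: "the patient should remain under the supervision of the Investigator or designee until the condition has returned to baseline or stabilized". There is no causality condition and no exit at a new therapy.
- **Section 9.3.** "Adverse Events of Special Interest for avapritinib are, regardless of grade or causality": cognitive effects and intracranial bleeding.
- **Table 1 (Schedule of Assessments).** The last column is EOT, with no day attached to it. Footnote k ends SAE and AESI collection at end of treatment, while Section 6.2.5 monitors adverse events to 30 days after the last dose.

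**The concern.** Section 2 gives long-term safety as the purpose of the study, and Section 10 treats these data as a continuation of each patient's record from the parent trial. For an AESI such as a cognitive effect, whether it persists or reverses after the drug is stopped is part of that record. A site holding this protocol finds two stopping rules for the same follow-up, one of which appears to leave out unrelated events, and no scheduled contact at which to apply either. Two sites could follow the same kind of event for different lengths of time and both be compliant. At stake is how complete the outcome data are for a very small cohort.

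**Working it through.** The plan states no figure on this point, so the check is a comparison of texts, followed by a rough scale.

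**Step 1. Which rule applies to an event ongoing at the last dose**

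| Why the patient stopped | Causality of the event | Section 4.6 | Section 8 (natural reading) | Result |
|---|---|---|---|---|
| This event | Related | To baseline or stabilisation | Same, or until a subsequent therapy starts | Conflict if the new therapy comes first |
| This event | Not related | To baseline or stabilisation | No follow-up rule | Section 4.6 alone |
| Another reason, e.g. progression | Related | Not triggered | To resolution or stabilisation, or until a subsequent therapy starts | May end unresolved at the new therapy |
| Another reason | Not related | Not triggered | No follow-up rule | No outcome follow-up required by either section |

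The gaps are in rows 1, 3 and 4. Events ongoing at the last dose are foreseeable, because Table 2 contains provisions under which dosing continues or resumes with a cognitive effect still present.

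**Step 2. Where follow-up would take place**

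Section 4.6 says "protocol-specified safety follow-up is to be performed", but Table 1 shows nothing after EOT. Section 3.1 mentions an End of Study evaluation; Table 1 has no column for it, and the only content given is the reason for discontinuation. Section 9.2 requires SAE follow-up information to be forwarded within 24 hours once the investigator receives it, but asks nobody to seek it, and it does not extend to non-serious AESIs.

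**Step 3. What is not affected**

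Section 10 summarises SAEs and AESIs by system organ class and preferred term. Within 30 days of the last dose an event is counted when it occurs, whatever its later course. No analysis of outcome or duration is planned, so no planned count changes.

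**Step 4. Scale**

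Inputs: about 5 patients (Section 4.1); 6 of 116 parent-study patients stopped for a treatment-related adverse event, and 30% had cognitive effects (Section 1.1.5). Applying those rates here is an assumption, since entrants are selected and exposure differs.

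- Stops for a related event: 6/116 = 5.2%, agreeing with the printed 5%. Expected number 5 × 0.0517 = 0.26. Chance of at least one: 1 − (110/116)^5 = 23%.
- Any cognitive effect: 5 × 0.30 = 1.5. Chance of at least one: 1 − 0.7^5 = 83%.
- One patient: 1/5 = 20% of the study.

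These figures only give an order of magnitude. An outcome is at risk only if the event is also ongoing at the last dose and falls in row 1, 3 or 4. The cognitive-effect rate in particular overstates the number affected. How many patients start another therapy, and when, is not given.

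**The case against.** The strongest reply is that Section 4.6 already covers the cases that matter most. An AESI that ends treatment triggers it, with no causality condition and no exit at a new therapy. The two sections can also be read together, with 4.6 governing care of the patient and 8 governing monitoring of the event. Section 8 itself ends at stabilisation or resolution, so the texts part only for an event still unstable when a new therapy begins. The limit to related events may be narrow: the word could attach to SAEs alone, and Section 9.5 makes related the default category ("The AE does not meet the criteria for" Not Related). All of this stands. It is why a reader who infers that outcomes of treatment-ending AESIs are definitely cut off goes too far: the text is contradictory there, not a settled truncation.

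Three other stronger inferences also fail:

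- **Fatal outcomes are lost.** Death is an SAE criterion. SAEs within 30 days are reportable whatever their cause, related ones after that too, and follow-up information received on an SAE must be forwarded.
- **The safety rates are biased.** The incidence summaries do not depend on the follow-up rule.
- **The EOT visit may be replaced by a call.** Footnote b's "This can be done by telephone if necessary" refers to recording the reason for stopping and the last dosing day. Table 1 still marks examination, vital signs and laboratory tests at EOT.

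Finally, ending follow-up at a new therapy has a rationale, since later changes are confounded by that therapy. This is a fair argument for either choice of end point, but not for having two. The reply also leaves rows 3 and 4 of the table unanswered.

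**Conclusion.** The point holds as an inconsistency with a limited consequence. Sections 4.6 and 8 give different end points, Section 8 on its natural reading omits unrelated events although AESIs are defined without regard to causality, and no scheduled contact exists after EOT to carry out the 30-day window or the follow-up that Section 4.6 refers to. Outcomes may go unrecorded for events not yet stable when a new therapy starts, and for events judged unrelated in patients who stop for another reason. The number affected is likely to be small, quite possibly none, but with about 5 patients each lost outcome is a fifth of the study. The conclusion rests on reading the word related in Section 8 as covering both SAEs and AESIs. If it covers SAEs only, unrelated AESIs are followed and the gap in row 4 shrinks to unrelated SAEs that are not AESIs; the difference in end points and the missing contact remain.

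**What to change.** 1. Reconcile Sections 4.6 and 8 so that one data-collection end point applies to events ongoing at the last dose, stated once and cross-referenced. Whether the start of a subsequent therapy ends collection is for the sponsor to decide and justify, but the answer should be the same in both places.
2. State that this end point covers all SAEs and AESIs regardless of causality, in line with Section 9.3.
3. Record the name and start date of any subsequent therapy, so that outcomes seen afterwards can be interpreted. Section 6.2.5 already collects concomitant medication to 30 days after the last dose, so the addition is small.
4. Add one telephone safety contact to Table 1 at the end of the existing 30-day window, identify it as the safety follow-up meant in Section 4.6, and use it to record the outcome of events ongoing at EOT. Bring footnote k into line with the 30-day window at the same time.

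The cost is a wording amendment and one call per patient, for about 5 patients. The drawback is some confounding of outcomes recorded after a new therapy starts, which the recorded start date makes visible. No dose or treatment rule changes.
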